4.8 Data Management

The CRO is responsible for all data management functions and documents related to this Registry (See Section 11.2 for detailed CRO responsibilities). The CRO's EDC database system will be designed to provide data entry, editing, and quality control, integrated with data management functions.

5. CLINICAL METRICS

The following clinical metrics will be used to measure the standard clinical outcomes and treatment emergent events that will be assessed through this Registry:

5.1 Tumor Assessments and Response

The tumor responses to HD IL-2 treatment will be determined by the site PI. Tumor responses will be assessed and categorized as CR, PR, SD, or PD using either RECIST or WHO criteria per site's standard procedure*. The sites will be required to indicate which criteria were employed in each patient's tumor assessments.

* PET scan may be used to confirm a CR or a conversion of a PR to a CR. There may also be surgical conversion of a PR to a CR. The site staff will adequately document these conversion cases on the case report forms for inclusion in the database.

Best Overall Response (BOR):

BOR is defined in this Registry as the investigator determined best response, occurring at or prior to Month 3; if the BOR is CR, PR, or SD, response since the last evaluation and TTP (first progression after Proleukin will be evaluated at standard of care interval visits (approximately every 6 months) until disease progression.

5.2 Patient Survival

Overall Survival (OS):

The OS is defined as the time from initiation of HD IL-2 treatment until patient death for any reason

Progression Free Survival (PFS):

PFS in this Registry is defined as the time from initiation of HD IL-2 treatment until disease progression or death.

5.3 Treatment Emergent Events

Treatment emergent events are defined as changes in specific features occurring during and shortly after HD IL-2 administration.

Treatment Emergent Mortality (TEM):

TEM is defined as patient death occurring from Day 1 of HD IL-2 administration until 2 weeks after the last dose of HD IL-2.

Other treatment emergent events of interest will include, at a minimum, the following:

- Number of doses administered per cycle
- Cause(s) for concluding dosing each cycle
- Number of cycles administered
- Cause(s) for discontinuing HD IL-2 therapy

6. ANNUAL DATA OUTPUT SUMMARY

It is anticipated that a report will be generated on an annual basis in order to track the status of the registry database and have an executive summary on current use of IL-2 and outcomes. The following data will be included in the annual summary.

- Number of sites in the PROCLAIMSM Registry
- Number of patients enrolled (total, mM, and mRCC)
- Number of patients treated with HD IL-2 alone
- OS and PFS

- Investigator-determined ORR at 3-month assessment
- Number of dose per HD IL-2 treatment cycle
- Number of HD IL-2 cycles received per patient
- Causes of discontinuation of HD IL-2 treatment

7. QUERIES OF THE REGISTRY DATABASE

7.1 Request for Data Access

The PROCLAIMSM Registry database may be made available to research investigators both within and outside the registry network. The RSC is responsible for defining the policies and procedures for data query and analysis, data sharing with others, and registry data publications.

7.2 Query Review and Approval

A data request to use the registry database will be reviewed and approved by the RSC to ensure that the query is scientifically sound, strategically feasible, and fits within the limits defined in this Registry, and is covered by the participant's informed consent.

A data extract plan will be prepared and the necessary data will be extracted from the database into a query-specific dataset for analyses. The data query is then added to the overall research portfolio of the registry database.

Data from these analyses will be shared with investigators upon request, but always as summarized, aggregate data. No identifying information will be released beyond a Registry ID number randomly assigned to each patient at the enrollment visit. At no time is an individual investigator given the names of participants, or the identity of the site where the patients were treated.

8. TYPES OF ANTICIPATED DATABASE QUERIES

Observational data queries may use the registry database for examining HD IL-2 therapy patterns including trends in care, comparative effectiveness and complications of treatment found in the patient population. Proposals for data provision must be submitted to the RSC for review and approval prior to data extraction or any additional data collection from the Registry. The following are the general types of anticipated data queries using the observational registry database:

- Changes in treatment patterns of HD IL-2
- Prognostic factors and patterns for HD IL-2 therapy
- Clinical responses to HD IL-2 therapy
- Late and rare effects of HD IL-2 therapy
- Long-term outcomes after HD IL-2 therapy
- Death incidence/relapse in patients received HD IL-2 therapy
- Persistence/resolution of complications after HD IL-2 administration
- Doses and cycle numbers of HD IL-2 in treated patients
- Reasons for HD IL-2 discontinuation
- Impact of site/patient specific features on treatment outcomes

- Success of different treatment models for the registry population
- Potential improvement of patient management in use of HD IL-2 therapy

9. SAFETY REPORT

9.1 Reporting

Sites enrolled in the PROCLAIMSM Registry are encouraged to report serious adverse events (SAEs) related to HD IL-2 treatment in compliance with the US Code of Federal Regulations. If Proleukin (Aldesleukin, HD IL-2) is a suspect or co-suspect drug reported on the FDA form 3500A Medwatch report, Prometheus laboratories requests a courtesy copy of the report. Within this reporting, Prometheus requests a courtesy copy Medwatch form of any deaths related to Proleukin treatment. Please e-mail or fax the courtesy copy to Prometheus Laboratories' drug safety department at [contact] or faxed to [name]. Please also include your contact information.

10. DISCLOSURE OF DATA AND PUBLICATIONS

10.1 Data Ownership and Confidentiality

All information provided by the registry will be held in strict confidence. Access to all information in the registry database will be tightly controlled with passwords and logins. Access to the registry database is limited to personnel based on their specific roles and responsibilities.

Patients will be assigned a unique identification number when the treatment center enrolls the patient into the PROCLAIMSM Registry. The identifying patient information, such as first and last name, social security number, contact phone number, and city, state and country may be verified at enrollment by the site staff to ensure that the patient has not been enrolled previously in the registry. A unique identification number is then assigned. The information will be maintained within the site's secure medical database which is separate from the registry database. These identifying data will not be included in data sets for analysis. The unique identification number contains no identifying information within it and will be used to track all information about the patient in the registry database.

The patient identity in the registry will be kept confidential at all times. Identifying information that will be included in the registry includes diagnosis date, birth date, treatment date and site. Data released to investigators outside the registry shall not include identifying data such as birth date and location of treatment, Sites will be assigned a unique identification number when initiated into the registry which will be used for reporting purposes. Public reporting of data will maintain the anonymity of both patients and sites.

All deliverables that come out of the registry database are considered confidential and may not be distributed without documented permission by the Sponsor (See "Data Sharing Policies" for more detailed instructions).

All research personnel participating in the PROCLAIMSM Registry will maintain up-to-date training in protection of human subjects.

10.2 Data Sharing and Publications

The registry data, either summary data and/or individual patient data, may be shared and published with agreement between the investigators and the Registry Steering Committee (RSC). An investigator who wishes to use data from the registry database must make a formal query request. The request is reviewed on the basis of scientific merit and feasibility.

Study results will not be published without the prior review and approval of the RSC. Authorship of manuscripts shall be in accordance with normal academic standards as described in the Uniform Requirements for Manuscripts Submitted to Biomedical Journals. Each party shall acknowledge the role of the other parties in all manuscripts. Potential coauthors will include members of the RSC, site investigators, and personnel from the Sponsor.

11. REGISTRY MANAGEMENT

11.1 Registry Oversight

A Registry Steering Committee (RSC) will be formed as a governance body to provide scientific oversight for the Registry, CRO and Sponsor). The RSC will act on behalf of the Sponsor and key stakeholder groups to oversee the feasibility, operations and the achievement of outcomes of the Registry.

A charter will be generated to define the responsibilities and scope of activities of the RSC, the composition and membership of the RSC, the purpose, timing and schedule of RSC meetings, and the relationship between RSC, Sponsor, and investigators. The RSC will be made up of between 4-6 members, with at least 1 member being a sponsor representative. Key opinion leaders will be invited to participate as RSC members and a chair person will be selected from amongst the members.

In practice, the RSC is responsible to carry out the following functions:

- Provide scientific and medical guidance on the design and conduct of the PROCLAIMSM Registry
- Hold periodical webinar and face to face committee meetings. Convene ad hoc meetings to monitor and review the registry progress and aggregate outcome data
- Control the scope of the PROCLAIMSM Registry by providing strategically and scientifically sound advice as emergent issues force justifications to be considered
- Review and approve research proposals using the database of the PROCLAIMSM Registry
- Define and oversee plan for use of data
- Make recommendations regarding data interpretation
- Approval and communication of the registry's deliverables

- Oversee completion and quality of the PROCLAIMSM Registry
- Nominate individuals to serve on the committee

11.2 Contract Research Organization Responsibilities

The CRO is responsible for site monitoring, data management, data extraction, and other relevant project management responsibilities. Safety reporting that is routed to the CRO, must be forwarded to the Sponsors DSPV group per section 9.0 of the protocol.

11.3 Sponsor Responsibilities

Prometheus Laboratories, Inc. is the Sponsor of the PROCLAIMSM Registry. The Sponsor is responsible for funding and managing the overall conduct of the registry program.

11.4 Principal Investigator Responsibilities

The Principal Investigator (PI) has the overall responsibility for patient treatment and management per site standard of care.

11.5 Access to Source Data/Documents

Site investigators in the Registry will allow clinical monitors from the Sponsor or the CRO direct access to all source data and documents including a patients complete medical record if necessary. Access must also be granted to authorized auditors, IRB reviewers, and all applicable regulatory bodies as necessary.

12. ETHICAL CONSIDERATIONS

The registry is to be conducted according to US and international standards of Good Clinical Practice, applicable government regulations and IRB policies and procedures.

12.1 Institutional Review Board

The registry protocol and any amendments will be submitted to an Institutional Review Board (IRB), in agreement with local legal requirements, for formal approval of the Registry. The IRB decision concerning the Registry will be made in writing to the investigator and a copy of this decision will be provided to the Sponsor before commencement of the registry. Copies of the IRB approved documents, as well as the IRB approval letters, will be retained in the Registry Trial Master File.

The site investigators will allow the IRB direct access to all relevant documents throughout the life cycle of the Registry. The IRB review will be conducted in accordance with all applicable regulatory requirements.

12.2 Informed Consent and Patient Protection

All patients in the prospective data collection will be provided written informed consent for participation in the Registry and release of their HIPAA compliant data to Prometheus and

the CRO for analysis.

The Informed Consent Forms (ICF) must be written in language readily understood by the patient. The ICF and any other related documents will be submitted with the protocol for review and approval by the IRB before the registry initiation. The formal consent must be obtained before any patient data can be entered into the registry database. The consent form must be signed by the patient or legal representative, and the investigator-designated site staff obtaining the consent. After informed consent is obtained, the original signed ICF copy will be retained in the investigator site records, and a copy will be provided to the patient.

In addition, the investigators and registry personnel will be responsible for complying with the Health and Information Portability and Accountability Act (HIPAA) requirements. The registry site is responsible for the accuracy and completeness of the data submitted and for ensuring all medical records are available to the clinical monitor, IRB auditors, and regulatory agents, as needed.

12.3 Record Retention

Per FDA and ICH GCP requirements, the RSC requires that all the registry-related documentation be retained for two years after the registry is closed or as mandated by the institution, whichever is longer. The investigator should contact Prometheus before any documentation is discarded.

13. SOURCE OF FUNDING

The PROCLAIMSM Registry will be supported by Prometheus Laboratories, Inc. as the Sponsor.

14. APPENDIX A: AN EXAMPLE REGISTRY DATABASE QUERY

Query Proposal #: 10PLK13-01

Proposal Title:

Treatment Related Mortality in Today's Clinical Practice in Patients with Metastatic Melanoma or Renal Cell Carcinoma Treated with High-Dose Interleukin-2: An Embedded, Controlled Analysis Using PROCLAIMSM Registry Database

1. BACKGROUND

Proleukin[®] (the brand name of aldesleukin for injection), also commonly known as interleukin-2 (IL-2) or recombinant IL-2 (rIL-2), was approved by US FDA in early 1990s for treating adult patients with metastatic melanoma (mM) or metastatic Renal Cell Carcinoma (mRCC). Today high-dose IL-2 remains as an effective immunotherapy for fighting cancers and have been used alone as well as in conjunction with chemotherapy and other treatment options. It is an efficacious yet toxic therapy as it works through patient's profound immune system to trigger tumor response. Over the years, despite the high mortality and severe morbidity rates initially produced, HD IL-2 can now be safely and effectively administered by experienced clinicians. It is crucial to have and adhere to a standard dosing and patient assessment criteria during IL-2 administration in order to manage symptoms and minimize toxicities⁷.

In the studies leading to the approval of Proleukin, the complete and clinical overall response rates (CR and ORR) in treating mM and RCC were reported to be 5-6% and 15-28% respectively, median Overall Survival (OS) of HD IL-2 were reported at 16-19 months for mRCC but only 4.5-8.8 months for mM, and treatment-related death rates were reported as 2% and 4% for mM and RCC respectively^{8, 9, 10}. All those data all collected from patients studied prior to 1998.

2. HYPOTHESIS:

We hypothesize that patient mortality in contemporary clinical practice is significantly lower than the historical data reported in initial clinical trials in 1990s on patients with mM or mRCC treated with HD IL-2 therapy.

3. SPECIFIC AIMS:

- To estimate the cumulative treatment emergent mortality (TEM) observed in patients treated with HD IL-2 for mM or mRCC using prospective data from the PROCLAIMSM Registry database.
- To compare the TEM derived from the PROCLAIMSM Registry in mM patients treated with HD IL-2 with historical mortality data.
- To compare the TEM derived from the PROCLAIMSM Registry in mRCC patients treated with HD IL-2 with historical mortality data.
- To compare the TEM derived from the PROCLAIMSM Registry between mRCC and mM in patients treated with HD IL-2.

4. DESIGN AND PROCEDURE:

The PROCLAIMSM Registry database will be the source of information to support all the data for fulfilling the query. One purpose of the registry database is to provide a research platform for researchers to study the real world treatment patterns and trends, as well as clinical outcomes, related to HD IL-2 therapy in patients with mRCC, mM or other malignancies in the United States. Treatment emergent mortality (TEM), which is defined as the incidence of patient death occurring from Day 1 of HD IL-2 administration until 2 weeks after the last dose of HD IL-2 with causality determined by the treatment physician, is standard data fields collected in the PROCLAIMSM Registry and will be the primary endpoint of this database query.

The primary endpoint will be analyzed for all patients and by stratifications for disease type (mM vs. mRCC). If a statistical difference is found in mortality rate comparison between this analysis dataset vs. historical data in Proleukin Prescription Information, analysis will be further stratified for metastatic sites, toxicity experience, line of treatment, and other ad hoc strata. The study outcomes will be compared to historical data as reported in the Prescription Information and literature, where such information exists.

The study will also examine incidence of treatment emergent death and overall survivals as time-dependent and patient-dependent variables and the cause of death between the two disease indications (mM vs. mRCC).

5. PATIENT POPULATION:

All prospective patients in the PROCLAIMSM Registry

6. ENDPOINTS:

The primary outcome is treatment emergent mortality (TEM). TEM is defined as the incidence of patient death occurring from Day 1 of HD IL-2 administration until 2 weeks after the last dose of HD IL-2 with causality determined by the treatment physician. The death event will be summarized by the cumulative incidence rate with disease types as stratification factors.

7. STRATIFYING FEATURES TO BE ANALYZED:

The TEM comparisons between data derived from the PROCLAIMSM Registry vs. historical data may be stratified for multiple tiers of analyses by the following features:

7.1 Patient related:

- Gender
- Age
- Weight and height
- Ethnicity
- Race
- ECOG score
- First Dose of HD IL-2 date

7.2 Disease related:

- Initial diagnosis date
- Disease type
- Metastasis
- Stage/remission status at enrollment
- Prior cancer therapies
- Surgery history
- Line of treatment with HD IL-2 (1st versus 2nd, 3rd ...)

7.3 HD IL-2 treatment related (for each cycle):

- Dosing start date
- Dose received
- Dose frequency
- Number of doses received
- Other interval cancer therapy received
- Toxicity experienced
- Reason for dose discontinuation

7.4 Treatment assessment and survival follow-up:

- Investigator determined response
- Method of response assessment
- Patient interval survival status
- Patient death date, as applicable
- Reported as SAE? If yes, try to get case narrative via Proleukin safety monitoring report

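### Appendix A lets treatment emergent mortality be stratified by post-baseline and outcome features, which gives circular or distorted stratum rates

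*Protocol*

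**What the plan says.** Appendix A Section 6 defines the endpoint, with HD IL-2 as the drug at the point where the quote stops: "TEM is defined as the incidence of patient death occurring from Day 1 of HD IL-2 administration until 2 weeks after the last dose of". The treating physician judges causality. The end of the window therefore depends on how many doses the patient actually received.

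Two places set the strata, with different force.

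- **Section 4 (Design and Procedure)** is conditional but firm. The condition is "If a statistical difference is found in mortality rate comparison between this analysis dataset vs. historical data in Proleukin Prescription Information". Once it is met, "analysis will be further stratified for metastatic sites, toxicity experience, line of treatment, and other ad hoc strata". Of the three features named there, metastatic sites and line of treatment are baseline features; toxicity experience is not.
- **Section 7 (Stratifying Features)** is permissive. The TEM comparisons with historical data "may be stratified for multiple tiers of analyses by the following features". Section 7.3 then lists, among others, "Number of doses received", "Toxicity experienced" and the reason for stopping dosing. Section 7.4 lists "Investigator determined response", "Patient interval survival status" and the date of death.

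No landmark, time-dependent definition or other handling rule is attached to any of these features. Section 4 does mention time-dependent variables, but that sentence is about treatment emergent death and overall survival as outcomes, not about the strata.

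**The concern.** A stratum for a mortality rate should be fixed before the patient is at risk. If membership is settled during or after the risk period, it can be a consequence of the death being counted. The table then reports how patients were sorted, not how risk differs between them.

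Here TEM could be tabulated by dose count, reason for stopping, response or survival status. The result could suggest that few doses go with high mortality, or that responders are protected, when identical underlying risk would give the same pattern. The comparison is also with historical data, which the protocol states as one rate per disease (2% for mM, 4% for mRCC). A registry stratum selected on toxicity is not like-for-like with a rate over all treated patients.

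**Working it through.** **1. The plan's own figure.** Appendix A Section 8.1 gives 1381 (mM) and 276 (mRCC), at 80% power and α = 0.05, for historical rates p0 of 2% and 4% against an expected p1 of 1%. A one-sample test against a fixed rate, two-sided, with continuity correction, reproduces both:

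- n0 = [(1.960·√(p0(1−p0)) + 0.842·√(p1(1−p1))) / (p0−p1)]²; n = (n0/4)·[1 + √(1 + 2/(n0·(p0−p1)))]²
- mM: n0 = 1282.6, n = 1380.8, rounded up to 1381
- mRCC: n0 = 243.2, n = 275.5, rounded up to 276
- 20% dropout: 1381/0.8 = 1726.25, so 1727; 276/0.8 = 345; total 2072

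The sample size is not at fault here. The reproduction shows that the planned comparison is one registry proportion against one fixed rate per disease. Section 8.1 does not state sidedness; the two-sided form is the one that matches.

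**2. Expected deaths.** At 1%: 1381 × 0.01 = 13.8, about 14 in mM; 276 × 0.01 = 2.8, about 3 in mRCC.

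**3. How each listed feature relates to TEM.**

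| Feature (Appendix A) | Relation to TEM | Effect of stratifying |
|---|---|---|
| Survival status, death date (7.4) | Contain the endpoint | Circular: 0% in those alive through the window; every event among those who died |
| Number of doses, reason for stopping (7.3) | Death ends dosing | Deaths shift into the low-dose strata |
| Investigator response (7.4) | Usually assessed about 3 months after start (Protocol Section 4.7.2) | Patients who die earlier may have no assessment |
| Toxicity (Section 4 and 7.3) | On the path to death | Conditions on a step between treatment and outcome |
| Features in 7.1 and 7.2 | Largely known before the first dose | No such problem |

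**4. Size of the truncation effect (illustration; all inputs assumed).** The protocol gives no dose distribution. Assume every patient has the same death risk h at every dose, survivors stop for other reasons with probability s after each dose, and the maximum is K doses. Then:

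- Overall TEM = h·Σ[(1−h)(1−s)]^k for k = 0 to K−1
- TEM in those with fewer than K doses = h / [h + (1−h)s]
- TEM in those reaching dose K = h
- Ratio = 1 / [h + (1−h)s]

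Setting h so that overall TEM is 1%:

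| K | s | TEM, fewer than K doses | TEM, K doses | Ratio |
|---|---|---|---|---|
| 14 | 2% | 3.92% | 0.08% | 48 |
| 14 | 5% | 1.93% | 0.10% | 20 |
| 14 | 10% | 1.29% | 0.13% | 10 |
| 28 | 2% | 2.28% | 0.05% | 49 |
| 28 | 5% | 1.30% | 0.07% | 20 |
| 28 | 10% | 1.05% | 0.11% | 10 |

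Risk per dose is identical throughout, so the whole gap is an artefact of counting doses after the fact. The values of K and s serve only to show a range; they are not taken from the protocol and imply nothing about treatment.

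**5. Precision of legitimate strata.** Exact 95% intervals: 14/1381 = 1.01% (0.56% to 1.70%); 3/276 = 1.09% (0.22% to 3.14%). If the mRCC group is split into halves of 138 with 1 and 2 deaths, the rates are 0.72% (0.02% to 3.97%) and 1.45% (0.18% to 5.14%). These can be estimated, but imprecisely.

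**The case against.** The best defence is that little of this is binding. Appendix A is an example query, subject to Steering Committee approval and a data extract plan. Section 8.2 leaves statistical analysis to each case, so handling rules may exist in a document not shown. Section 7.4 also carries items such as whether the death was reported as an SAE, so it reads partly as a list of fields to extract under an ill-chosen heading. All of this lowers the weight. It does not remove the point, because the text itself names these features as strata for TEM, and the example is what later proposals will be modelled on.

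Several stronger readings are tempting and should not be drawn.

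- *That TEM is required to be stratified by all these features.* Only toxicity carries a firm commitment, and only after a difference is found. The rest are optional.
- *That death determines every one of them.* This is literal for survival status and death date, and works by truncation for doses and by missing assessment for response. Toxicity precedes death; the problem there is conditioning on an intermediate step.
- *That TEM is zero among responders by construction.* The window follows the last dose, Protocol Section 5.1 allows best response at or before Month 3, and Section 4.7.2 records whether therapy continues. A responder can die inside the window. A bias is plausible; a structural zero is not.
- *That historical rates cannot be broken down this way.* The sources are not at hand, and Section 4 limits the comparison to information that exists.
- *That mRCC strata cannot be estimated with about 3 deaths.* They can, with wide intervals.
- *That the significance condition is an error.* Holding back exploratory strata until an overall difference appears is a defensible restraint.

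**Conclusion.** The point holds, limited to the stratified tables. Following Appendix A Sections 4 and 7 as written gives circular rates for survival status and death date. Rates by dose count, reason for stopping and response can differ without any difference in risk, and conditioning on toxicity biases the comparison with a single historical rate per disease.

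The circularity and the direction of the dose-count effect follow from the definitions alone. The 10- to 49-fold range does not: it rests on constant risk per dose, overall TEM of 1%, and assumed dose maxima and stopping rates. The response effect depends on how many TEM deaths precede the assessment, which the protocol does not give.

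The primary TEM rate, overall and by disease type, and the sample size are untouched. This should be corrected, but it concerns secondary tables in an example query.

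**What to change.** In Appendix A Sections 4 and 7:

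1. Limit stratification of TEM to features known before the first dose: those in 7.1 and 7.2, such as disease type, ECOG score, metastatic sites and line of treatment. Protocol Section 4.5.1 allows enrolment during or after the initial course, so say that the pre-dose value is used.
2. Remove toxicity experience from the Section 4 strata.
3. Relabel 7.4 as outcome data.
4. Report the 7.3 features, including toxicity, as a descriptive listing of deaths, or analyse them only by landmark or as time-dependent variables.
5. Give each stratum rate with an exact 95% confidence interval, and note that the intervals will be wide at the expected number of deaths.

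The cost is a change of wording and fewer exploratory tables. No new data are needed.
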